### National Eye Institute Vision-related Quality of Life Questionnaire

Evaluation of the NEI-VFQ-25 questionnaire will follow the description provided by Mangionec. First, response categories for each provided answer will be converted into scores ranging from 0 to 100 according to the official scoring key. These scores will then be averaged among all items belonging to the same subscale. Subscale scores will only be calculated if at least one of the contributing items was answered. A total of 12 subscale scores may be calculated, with missing items not being considered during averaging. Furthermore, the composite score which is defined as average of all vision-targeted subscale scores, excluding the general health rating, will be calculated.

---

c Mangione, C.M. (2000): National Eye Institute 25-Item Visual Function Questionnaire (VFQ-25), Version 2000: NEI VFQ-25 Scoring Algorithm

Subscale scores and composite score as well as their change over time will be summarized by visit using summary statistics.

#### Device deficiencies

The analysis of device malfunctions is already described in Section 7.5. All other device deficiencies will be listed only.

#### External eye photography

The analysis of external eye photography is not part of this SAP but will be done by the Sponsor.

#### Slit-lamp biomicroscopy

All assessments will be listed only. Noteworthy abnormal findings will be reported as adverse events and will be analyzed as part thereof.

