5.3 Risks and anticipated Adverse Device Effects to be assessed

Information will be collected on all ADEs. Particular attention will be paid to the following AEs (AEs of special interest):

- Signs of toxicity of the implant
- Uncontrolled increase in IOP
- Changes in anterior chamber structures including ACD and ACA
- Anterior chamber inflammation (Tyndall/flare/anterior chamber cells)
- Fibrin reaction (e.g. anterior chamber fibrin, fibrin deposition on lens)
- Corneal endothelial cell loss
- Pigment dispersion
- Iris transillumination defect

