6.4.4.13 Anterior Segment Evaluation

External Eye Photography (Slit-lamp)

External eye photography will be performed in order to document potential changes to the anterior segment of the eye involving the conjunctiva, cornea, iris (e.g. iris transillumination) or pupil structure.

 Implantata Ophthalmic Products GmbH	Clinical Investigation Plan ARGOS-03	Revision C Page 35 of 67
--------------------------------------------------------------------------------------------------------------------------	-------------------------------------------------------	---------------------------------

Slit-lamp Biomicroscopy

Slit-lamp biomicroscopy involves the examination of the external eye and anterior segment structures. The following anatomic parameters will be assessed by using the slit-lamp biomicroscopy:

- a) Lids
- b) Conjunctiva (*irritation*)
- c) Cornea (*edema, Descemet folds*)
- d) Anterior chamber (*cells/flares (SUN-Classification), fibrin, flattening*)
- e) Iris (*transillumination, pigment dispersion*)
- f) Pupil
- g) Lens
- h) Anterior vitreous (*cells/haze (NIH-Grading)*)

Optical Coherence Tomography (OCT)

Standard anterior segment OCT will be used to evaluate effects on change in chamber angle and to assess the central corneal thickness. A change of the OCT device should be avoided during the study.

Confocal Microscopy

standard confocal microscop will be to determine corneal endothelial cell density.

A change of the should be avoided during the study.

Gonioscopy

Standard gonioscopy will be used to confirm glaucoma classification and to assess other problems within the anterior chamber, such as the presence of foreign bodies hidden in the recess of the angle. The gonioscopic grading system according to Shaffer is used in this study.

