7.1.6 Additional Outcome Variables

- Best corrected visual acuity at each visit (both eyes).
- Scores for the National Eye Institute Vision-related Quality of Life Questionnaire – VFQ-25 at the respective visit.
- Device deficiencies.
- External eye photography results at each visit (both eyes)
- Slit-lamp biomicroscopy results at each visit (both eyes)
- Corneal endothelial cell density results at each visit (both eyes)
- Gonioscopy results at each visit (both eyes)
- Funduscopy results at each visit (both eyes)

 Implantdata Ophthalmic Products GmbH	Clinical Investigation Plan ARGOS-03	Revision C Page 44 of 67
---------------------------------------------------------------------------------------------------------------------------	-------------------------------------------------------	---------------------------------

- IOP self-measurements

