7.2.6 Analysis of Additional Outcome Variables

For all additional outcome variables, except for the IOP self-measurements and device deficiencies, summaries will be provided per visit and eye or, in case of the VFQ-25, only per visit. Further details about the analysis of additional outcome variables will be provided in the SAP.

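### SAP 7.8 only lists slit-lamp findings, although CIP 7.2.6 promises summaries by visit and eye; within the SAP, four of the eight CIP 5.3 risks are therefore summarised only through AE reporting

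*SAP*

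**What the plan says.** **Protocol (CIP).** Section 7.1.6 names as an additional outcome variable "Slit-lamp biomicroscopy results at each visit (both eyes"). Section 7.2.6 then commits to an analysis: "For all additional outcome variables, except for the IOP self-measurements and device deficiencies, summaries will be provided per visit and eye" (for the VFQ-25, per visit only). It leaves further details to the SAP. Section 7.2 adds that variables recorded for both eyes are analysed separately by eye so that the study eye and fellow eye can be compared.

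**SAP.** Section 6.6 keeps slit-lamp results among the variables to be evaluated. Section 7.8 reads "All assessments will be listed only" and continues "Noteworthy abnormal findings will be reported as adverse events and will be analyzed as part thereof". The appendix provides a slit-lamp listing (12.2.8.4.1) but no slit-lamp table under 8.4.3. Section 8 declares one change from the CIP, which concerns the IOP agreement analysis.

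**The concern.** Long-term safety is a primary objective, and CIP 5.3 singles out eight risks: "Particular attention will be paid to the following AEs (AEs of special interest"). Several of them are things an examiner sees at the slit lamp. If those examinations are not tabulated, the SAP's summary evidence on them comes only from what the investigator chose to report as an adverse event. The study has no blinding (SAP 2.8), and the SAP does not define which findings are noteworthy.

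At stake are a descriptive picture of chronic inflammation and pigment release over three years, the same picture in the fellow eye, and the traceability of a departure from the CIP.

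**Working it through.** The plan gives no figure to reproduce, so the check compares the texts and then counts.

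**Step 1. Is slit-lamp covered by the commitment?** CIP 7.1.6 includes it. CIP 7.2.6 excepts only IOP self-measurements and device deficiencies. It is covered.

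**Step 2. Which CIP 5.3 risks are slit-lamp items in CIP 6.4.4.13?**

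- Anterior chamber inflammation and fibrin reaction match "Anterior chamber (*cells/flares (SUN-Classification), fibrin, flattening".
- Pigment dispersion and iris transillumination defect match "Iris (*transillumination, pigment dispersion".
- The other four are signs of toxicity, uncontrolled IOP increase, changes in anterior chamber structures and endothelial cell loss. They are not counted here, although chamber flattening could also bear on the third.

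Result: 4 of 8. Among these four, the CIP names a grading scale only for cells and flare (SUN).

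**Step 3. How does the SAP treat comparable examinations?**

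| Examination | SAP output by visit and eye |
|---|---|
| Funduscopy (7.8) | Frequencies; denominator is subjects attending the visit |
| Gonioscopy (7.8) | Frequencies |
| Endothelial cell density (7.8) | Summary statistics and change |
| Slit-lamp (7.8) | Listing only |

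**Step 4. What does the AE route keep, and what does it drop?**

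- *Kept:* SAP 7.7 tabulates eye-related AEs by SOC and PT, worst severity, seriousness and eye. It gives a rate per 10 patient-years with an exact 95% interval for AEs of special interest.
- *Stable findings:* CIP 9.1.2 asks patients about new or worsening problems and adds events that are observed or spontaneously reported. A finding already present and unchanged since V01 may therefore not be entered. CIP 6.4.3.1 does mention ongoing device effects, and a site could record such a finding as a concomitant disease. Hence may, not will; and the concomitant-disease table is not by visit or eye.
- *Grade:* CIP 9.1.2 rates AE severity by tolerability and interference with usual activities, which is not the SUN scale.
- *Course:* SAP 7.7 collapses an event that changes severity into one event at its worst severity, so there is no visit-by-visit comparison between eyes.

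**Step 5. Extent.** Maximum enrolment is 5 + 21 = 26 (CIP 7.2.7). With 7 visits and both eyes examined, 26 x 7 x 2 = 364 eye examinations, of which 26 x 7 = 182 are of the study eye. This is an upper bound that assumes full enrolment and attendance.

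**Step 6. Is the change declared?** SAP 2.11 wants changes from the CIP justified and documented at least in the SAP text. For the agreement analysis, SAP 7.5 says outright that it differs from the CIP. SAP 7.8 gives a partial reason for listing slit-lamp data (noteworthy findings go to AEs) but does not call it a change. Section 8 does not mention it.

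**The case against.** The case for leaving the SAP alone has real weight.

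- **AE counting is the CIP's own design.** CIP 5.3 calls these risks AEs, the primary safety variable is the incidence of device-related AEs, and slit-lamp is only an additional variable in an exploratory study. This stands: counting the risks as AEs is not the error. The error is omitting the further summary that CIP 7.2.6 promises.
- **The data are not lost.** They are listed by eye and visit, and 26 patients can be read by hand. This stands in part. The listing's title refers to abnormalities, so normal examinations, and with them the denominators, may not appear.
- **Iris transillumination has a second source.** External eye photography documents it, but the SAP leaves that analysis to the Sponsor and states no method.
- **The SAP is open about the choice.** SAP 2.11 does not name Section 8, and 7.8 is SAP text. This stands in part: the choice is visible, but it is not identified as a departure.
- **The SAP cites CIP revision B, and the CIP supplied is Revision C.** Whether 7.2.6 read the same in revision B cannot be checked. The SAP should still agree with the current CIP.

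A reader might infer that these four risks produce no safety result, or that AE reporting is known to under-count them. The documents support neither. SAP 7.7 tabulates them when reported, and the earlier pigment dispersion figures (5 of 6 in ARGOS-01, 8 of 22 in ARGOS-02; CIP 4.2) were themselves AE reports. The ARGOS-02 fibrin cases followed surgery and say little about late follow-up. A table would not remove open-label judgement either, because the examiner is equally unmasked; it removes only the further decision whether a finding counts as an AE.

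**Conclusion.** The point holds as a mismatch between the CIP and the SAP. A promised summary by visit and eye is replaced by a listing without being identified as a change, and four of the eight CIP 5.3 risks are left with AE tables as their only summary within the SAP. Up to 364 eye examinations go unsummarised.

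The number of findings that would escape the AE tables cannot be calculated, because the documents give no share of slit-lamp findings that become AEs. The loss that follows from the texts is one of form: the SUN grade, the per-visit denominators and the visit-by-visit comparison of the two eyes. The possible loss of stable V01 findings depends on how sites record them. The correction is worth making because it is inexpensive and bears on a primary objective, but the primary safety analysis does not fail without it.

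**What to change.** In SAP 7.8, replace the listing-only sentence with wording to this effect: absolute and relative frequencies of slit-lamp findings will be given by visit and eye, using the categories recorded in the eCRF (SUN grade for cells and flare; presence or category as recorded for fibrin, pigment dispersion and transillumination), with the number of subjects attending the visit as denominator, as for funduscopy.

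Keep the listing and the AE analysis, and add the table to appendix 8.4.3. A shift table from V01 is optional; the CIP does not promise one for this variable. If the Sponsor prefers listing only, the minimum is a sentence in SAP 7.8 or Section 8 that identifies this as a change from CIP 7.2.6 and justifies it.

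The cost is a change of SAP wording and one or two tables from examinations already scheduled, with no new visit or procedure. This assumes that the eCRF, which is not among the documents, holds the findings in coded fields; free text would need coding first. If the database is already closed, SAP 2.11 requires the change to be justified and documented at least in the final clinical investigation report.

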#### Funduscopy

Frequency (absolute and relative) of funduscopy abnormalities as well as abnormality details will be displayed for each examined area (macula, retina, optic nerve, other) by visit and eye. The denominator for the relative frequency will be the number of subjects attending the respective visit.

#### Gonioscopy

Frequency (absolute and relative) of Gonioscopy results will be displayed by visit and eye.

#### Corneal endothelial cell density

Summary statistics (raw values and change over time) for corneal endothelial cell density will be provided by visit and eye.

#### Central corneal thickness

Summary statistics (raw values and change over time) for central corneal thickness will be provided by visit and eye.

#### Comparative measurements performed in the clinic between study end of ARGOS-01/ARGOS-02 and Visit 01 (GAT vs. ARGOS-IO)

Values for comparative measurements performed in the clinic between study end of ARGOS-01/ARGOS-02 and Visit 01 (GAT vs. ARGOS-IO) will be listed since only a few data are expected.

### Position of IOL and ARGOS-IO pressure sensor

Frequency (absolute and relative) of whether the IOL/ARGOS-IO pressure sensor were still in situ will be provided by visit.

### IOP self-measurements

Analysis of IOP self-measurements is not within scope of this SAP and will be described at least in the clinical investigation report if results are included.

## 7.9 Special Analytical Issues

### Unscheduled visits

Unscheduled visits may be performed, as necessary, to ensure the safety and well-being of subjects. Data from these visits will only be included in the patient listings but not in the statistical analysis tables and figures with the following exceptions:

- AEs
- Device deficiencies
- Concomitant medications
- Number of unscheduled visits due to increased self-measured IOP

## 8. Changes in the Planned Analysis

As only one series of measurements of IOP per type of IOP measurement and visit is available, the description of the analysis of the primary endpoint has been adapted to cover this case, in line with the guidance provided by Zhou et al., 2011.

## APPENDIX

### Tables

#### 8.1 Study subjects

- 8.1.1 Disposition of subjects
  - 8.1.1.1 Number of subjects enrolled
  - 8.1.1.2 Number of subjects per visit
  - 8.1.1.3 Duration of study participation
- 8.1.2 Demographics and other patient characteristics
- 8.1.3 Medical history and concomitant medication
  - 8.1.3.1 Medical history by SOC and PT
  - 8.1.3.2 Concomitant diseases by SOC and PT
  - 8.1.3.3 Concomitant medications by ATC level

#### 8.2 Performance

- 8.2.1 Comparison of intraocular pressure measurements (IOP)
  - 8.2.1.1 IOP measurements with ARGOS-IO and comparators by visit
  - 8.2.1.2 Limits of agreement between IOP measurements with ARGOS-IO and comparators by visit
  - 8.2.1.3 Limits of agreement between IOP measurements with ARGOS-IO and comparators by subgroup and visit
- 8.2.2 Device malfunctions
  - 8.2.2.1 Summary of device malfunctions
  - 8.2.2.2 Summary of device malfunctions by subgroup
  - 8.2.2.3 Device malfunctions per 10 patient years
- 8.2.3 Glaucoma progression by visit
- 8.2.4 Change in glaucoma medication
  - 8.2.4.1 Summary of changes in glaucoma medication
  - 8.2.4.2 Changes in glaucoma medication per 10 patient years
- 8.2.5 Unscheduled visits due to self-measured increased IOP

#### 8.3 Safety data

- 8.3.1 Adverse Events (AEs) and device related adverse events (ADEs)
  - 8.3.1.1 Overall summary of AEs
  - 8.3.1.2 Overall summary of ADEs
  - 8.3.1.3 Subjects with eye-related AEs and number of eye-related AEs by SOC and PT
  - 8.3.1.4 Subjects with eye-related ADEs and number of eye-related ADEs by SOC and PT
  - 8.3.1.5 Subjects with eye-related AEs by worst severity, SOC and PT
  - 8.3.1.6 Subjects with eye-related ADEs by worst severity, SOC and PT
  - 8.3.1.7 Subjects with eye-related AEs by seriousness, SOC and PT

- 8.3.1.8 Subjects with eye-related ADEs by seriousness, SOC and PT
- 8.3.1.9 Eye related ADEs per 10 patient years
- 8.3.2 Deaths and other serious / significant adverse events
- 8.3.2.1 Serious AEs, listing of subjects
- 8.3.2.2 Deaths, listing of all serious AEs of subjects who died
- 8.3.2.3 AEs leading to discontinuation, listing of subjects

8.4 Other data

- 8.4.1 Visual acuity assessments by eye and visit
- 8.4.2 Results of the National Eye Institute Vision-related Quality of Life Questionnaire (NEI VFQ-25) by visit
- 8.4.3 Ophthalmic examinations
  - 8.4.3.1 Abnormalities detected by funduscopy by eye and visit
  - 8.4.3.2 Gonioscopy results by eye and visit
  - 8.4.3.3 Central corneal thickness and corneal endothelial cell density by eye and visit
- 8.4.4 Position of IOL and ARGOS-IO pressure sensor

The selection, naming and numeration of the tables is not mandatory but might be adapted in accordance with the described analyses in this SAP.

## Figures

- 8.1 Study subjects
- 8.1.1 Flow chart of study disposition
- 8.2.1 Comparison of intraocular pressure measurements (IOP)
  - 8.2.1.1 Limits of agreements between ARGOS-IO and Goldmann applanation tonometry (GAT)
    - 8.2.1.1.1 Bland-Altman Plot (ARGOS-IO vs. GAT), Visit 01
    - 8.2.1.1.2 Bland-Altman Plot (ARGOS-IO vs. GAT), Visit 02
    - 8.2.1.1.3 Bland-Altman Plot (ARGOS-IO vs. GAT), Visit 03
    - 8.2.1.1.4 Bland-Altman Plot (ARGOS-IO vs. GAT), Visit 04
    - 8.2.1.1.5 Bland-Altman Plot (ARGOS-IO vs. GAT), Visit 05
    - 8.2.1.1.6 Bland-Altman Plot (ARGOS-IO vs. GAT), Visit 06
    - 8.2.1.1.7 Bland-Altman Plot (ARGOS-IO vs. GAT), Visit 07
    - 8.2.1.1.8 Bland-Altman Plot (ARGOS-IO vs. GAT), overall
  - 8.2.1.2 Limits of agreements between ARGOS-IO and PASCAL dynamic contour tonometer (DCT)
    - 8.2.1.2.1 Bland-Altman Plot (ARGOS-IO vs. DCT), Visit 01
    - 8.2.1.2.2 Bland-Altman Plot (ARGOS-IO vs. DCT), Visit 02

8.2.1.2.3	Bland-Altman Plot (ARGOS-IO vs. DCT), Visit 03
8.2.1.2.4	Bland-Altman Plot (ARGOS-IO vs. DCT), Visit 04
8.2.1.2.5	Bland-Altman Plot (ARGOS-IO vs. DCT), Visit 05
8.2.1.2.6	Bland-Altman Plot (ARGOS-IO vs. DCT), Visit 06
8.2.1.2.7	Bland-Altman Plot (ARGOS-IO vs. DCT), Visit 07
8.2.1.2.8	Bland-Altman Plot (ARGOS-IO vs. DCT), overall

The selection, naming and numeration of the figures are not mandatory but might be adapted in accordance with the described analyses in this SAP.

## Listings

12.2	Subject data listings
12.2.1	Disposition of subjects
12.2.1.1	Site numbers and principal investigators
12.2.1.2	Informed consent
12.2.1.3	Visit dates and discontinuation
12.2.2	Protocol deviations
12.2.3	Demographics and other patient characteristics
12.2.4	Medical history and concomitant diseases
12.2.4.1	Medical history
12.2.4.2	Concomitant diseases
12.2.5	Concomitant medications
12.2.5.1	Glaucoma medication
12.2.5.2	Other concomitant medications
12.2.6	Performance
12.2.6.1	IOP measurements by visit
12.2.6.2	Device malfunctions
12.2.6.3	Glaucoma progression by visit
12.2.6.4	Unscheduled visits
12.2.7	Safety data
12.2.7.1	Adverse events listing
12.2.8	Other data
12.2.8.1	Best corrected visual acuity by eye and visit
12.2.8.2	National Eye Institute Vision-related Quality of Life Questionnaire (NEI VFQ-25) by visit
12.2.8.3	Device deficiencies
12.2.8.4	Ophthalmic examinations
12.2.8.4.1	Abnormalities detected by slit-lamp microscopy by eye and visit

- 12.2.8.4.2 Abnormalities detected by funduscopy by eye and visit
- 12.2.8.4.3 Gonioscopy results by eye and visit
- 12.2.8.4.4 Other examinations
- 12.2.8.5 Position of IOL and ARGOS-IO pressure sensor by visit
- 12.2.8.6 Comparative measurements performed in the clinic between study end of ARGOS-01/ARGOS-02 and Visit 01 (GAT vs. ARGOS-IO)

The selection, naming and numeration of the listings is not mandatory but might be adapted in accordance with the described analyses in this SAP.
